than mild (i.e. if they report moderate or severe side effects), a medical professional (i.e. nurse or physician) will follow up to confirm that they are ok to complete the MRI and provide care as needed. All participants will complete a breathalyzer and saliva drug test to confirm sobriety. Females will be asked to provide a urine sample for a pregnancy test. Participants will then complete an MRI and the Alcohol Purchase Task. They will be sent home with 5 days' worth of capsules. They will return after 5 days and repeat the same procedures.

- a. Dosing. We will administer doses of naltrexone and placebo. Dosing will be double-blind and counter balanced. Participants will receive 5 capsules on their first visit to take during the week. They will receive 5 additional capsules to take each day of the following week. Naltrexone will be over-encapsulated by the Investigational Drug Service at the School of Pharmacy. Matching placebo capsules will contain methylcellulose powder. Naltrexone will be taken once daily by mouth and ramped up by the following schedule: Monday-25mg, Tuesday-25mg, Wednesday-50mg, Thursday-50mg, Friday-50mg. A study coordinator blind to the contents of the capsules will deliver the capsules to the participant. The Investigational Drug Service will maintain blinding and will track dosage, to be revealed following study completion. Half of participants will receive placebo during week 1 and half will receive placebo during week 2. Remote video monitoring will also be used to assess adherence. Participants will receive a text message on their mobile phones at 9 am each morning reminding them to take the medication and instructing them to upload a video of themselves doing so to a secure data repository (REDCap). A study-provided mobile phone will be available for participants who do not own a mobile phone or who are not willing to use their phone for this purpose (i.e., due to concerns about mobile data cost). The digital timestamps of these videos will subsequently be extracted, and their contents reviewed, to verify that the participant ingested the medication at the instructed time. Other studies of non-treatment-seeking individuals have reported success with remote video monitoring (DeWorsop et al. 2016).

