- ii. **Emotion Regulation task:** In the emotion regulation task (Waugh et al. 2016), we will examine subjects' ability to change how they are feeling by changing the way they think. Participants will be shown a series of pictures from the International Affective Picture System that have been validated and grouped by rating (e.g. typically induces negative affect) (Lang, Bradley, and Cuthbert 1997). Some pictures are designed to be neutral, such as pictures of nature scenes, and some are designed to evoke strong negative feelings, such as disgust or horror. Prior to viewing each picture, the participant will be instructed to either "Look" or "Decrease". When instructed to "Look", participants are told to keep their eyes on the picture and feel any feelings naturally without trying to change them. This instruction occurs prior to all 15 neutral pictures and prior to 15 of the negative pictures. When instructed to "Decrease" prior to the remaining 15 negative pictures, participants are told to keep their eyes on the picture and find an aspect of it that is not as bad as it seems at first. After viewing each image, participants will be asked how negative they feel. They will be shown a five-point Likert scale from one (not at all) to five (extremely negative), and they will record their response by pressing one of five buttons on a button box attached to their hand. Two sets of pictures will be available so that each participant will see a new set of images on each scan. Order of the sets will be counterbalanced across participants.

[figure not shown]

Figure 3: This figure shows the presentation of the cues for the Social Task used

- iii. **Social Task:** The task, adapted from Jepma et al and Willroth et al, requires participants to rate their expected and experienced valence of varying types of images (Fig. 3). Three distinct geometric shapes acted as cues that predicted the category of image that the individual would subsequently view (erotic, non-erotic pleasant, or neutral). On presentation of the cue, the subject is asked to rate the expected valence of the image using a slider device on a scale of unpleasant to pleasant (coded as 0 to 100). After rating their expectation, they

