E. Potential Scientific Problems: One challenge of our study is that we will not directly observe naltrexone binding. Directly observing naltrexone's activity would require PET imaging to observe displacement of a tracer that binds to opioid receptors, but we will not do that in this study due to cost and time. Thus, even if we observe behavioral or neural effects, we will not know if naltrexone is acting at that site. However, since we are using a randomized, placebo-controlled design, we can still draw conclusions about naltrexone causing the changes even if the changes may be downstream from naltrexone's direct site of action.

F. Data Analysis Plan: Outcomes will be examined using paired t-tests for two times (active medication, placebo). Functional MRI analysis will be conducted with AFNI software (Cox 1996). Functional images will be time-slice corrected and co-registered with anatomical images. Anatomical images will be non-linearly warped to standard space and an identical transformation will be applied to the functional image. Functional images will be blurred using a 4mm Gaussian kernel and values will be scaled to have a mean intensity of 100. A regression algorithm will be applied including six regressors to account for motion. For the monetary incentive delay task, regressors of interest include the gain, loss, and neutral cue. For the emotion regulation task, regressors of interest include neutral, look, and decrease conditions. For the monetary incentive delay task, activation will be extracted from the nucleus accumbens for each of the three cues. For the emotion regulation task, activation will be extracted from the amygdala for each of the three conditions. As an exploratory analysis, we will conduct whole-brain, voxel-wise analysis.

Sample Size and Power Considerations. In terms of evaluating differences in reward activation between placebo and mu-opioid antagonism conditions, a study of mice estimated a large effect size of mu-opioid antagonism on reward response in the nucleus accumbens, with Cohen's $d > 1.0$ (Walters et al. 2005). A study of kappa-opioid receptor modulation in human reward response measured with functional MRI found a medium to large effect size of Cohen's $d = 0.6$ (Krystal et al. 2020). We specified significance level alpha=.05, two-tailed, and power of 0.8. A sample of 9 adults would provide 80% power to detect an effect size of 1.0 or greater as significant.

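### The paired t-tests ignore period in a two-sequence crossover; a period term costs about one point of power at 5/5 and protects precision if week 1 and week 2 differ

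*Combined protocol and SAP*

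**What the plan says.** The design has two treatment orders. Section IV.C.a (Dosing) states: "Half of participants will receive placebo during week 1 and half will receive placebo during week 2". Section I gives 10 participants, hence 5 per order. For the second week, Section IV.C says: "They will return after 5 days and repeat the same procedures".

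The analysis in Section IV.F is one sentence for all three outcomes: "Outcomes will be examined using paired t-tests for two times (active medication, placebo"). Neither that section nor any other mentions a period, visit, sequence or order term. Order is handled by design alone: treatment order is counterbalanced, and for the Emotion Regulation task (Section IV.C.b.ii) so is the order of the picture sets: "Two sets of pictures will be available so that each participant will see a new set of images on each scan". No alternate form is described for the Monetary Incentive Delay task or the Alcohol Purchase Task.

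The order each person received will be known at analysis: "The Investigational Drug Service will maintain blinding and will track dosage, to be revealed following study completion".

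On power, Section IV.F says "We specified significance level alpha=.05, two-tailed, and power of 0.8", and then "A sample of 9 adults would provide 80% power to detect an effect size of 1.0 or greater as significant".

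**The concern.** Suppose all outcomes move by some amount between the first and second session, whatever the capsule. Familiarity with the scanner, a second run of the same speeded task or a second pass through the same price list could each do this. People who take placebo first then have that amount added to their naltrexone-minus-placebo difference, and people who take naltrexone first have it subtracted. Counterbalancing cancels the shift in the mean. It does not remove it from the spread of the differences, and that spread is the error term of the paired t-test.

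Power and interval width are therefore at stake in a study of about 10 people. Two features of this trial make precision matter more than usual:

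- Hypothesis 2 predicts no effect on the amygdala, so a test that is less able to reject makes that prediction look better supported than it is.
- Section IV.G says the data will support a further grant application. Period variance left in the SD of the differences would make the standardised effect look too small.

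**Working it through.** **The plan's own figure.** Reading the effect size as SDs of the paired difference, the exact two-sided paired t-test at alpha 0.05 and effect 1.0 has 74.8% power at n = 9 and 80.3% at n = 10. The normal approximation gives n = 7.85, so 8. The stated 9 lies between the two. The shortfall at exactly 9 is a separate matter; the planned 10 reaches 80%.

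**Inputs.** From the documents: n = 10, split 5/5; two-sided alpha 0.05; effect τ = 1.0. As an alternative I use τ = 0.6, the value in Section IV.F for which "A study of kappa-opioid receptor modulation in human reward response measured with functional MRI found a medium to large effect size", also read as SDs of the paired difference. Assumed: normal paired differences with SD 1, no carryover, and a week 1 to week 2 shift π of 0 to 1.0 SD. The documents give no shift, SD, within-person correlation or dropout rate.

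**Model.** With n1 people on placebo first and n2 on naltrexone first, the naltrexone-minus-placebo difference has mean τ + π in the first group and τ − π in the second.

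*Planned paired t-test.* The mean difference has expectation τ + π(n1 − n2)/n. The residual sum of squares is noncentral chi-square with n − 1 df and noncentrality 4π²n1n2/n. At 5/5 the noncentrality is 10π², so the expected variance estimate is 1 + 10π²/9. At π = 0.5 that is 1 + 2.5/9 = 1.278, an SD of 1.13 instead of 1. A true effect of 1.0 would then look like 1/1.13, about 0.88.

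*Period-adjusted analysis.* This compares the two orders on half the period differences. SE = 0.5√(1/n1 + 1/n2) = 0.5√0.4 = 0.316, with n − 2 = 8 df. The shift drops out.

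**Results at 5/5** (exact; a simulation of 400,000 trials per cell agrees within 0.002 for effects 1.0 and 0):

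| Shift (SD) | Paired power, τ = 1.0 | Paired power, τ = 0.6 | Paired type I error |
|---|---|---|---|
| 0 | 80.3% | 39.6% | 5.0% |
| 0.25 | 78.3% | 37.1% | 4.4% |
| 0.5 | 72.0% | 30.6% | 3.0% |
| 0.75 | 61.7% | 21.9% | 1.6% |
| 1.0 | 48.2% | 13.5% | 0.7% |
| Period-adjusted, any shift | 79.1% | 38.6% | 5.0% |

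Break-even shift: 0.196 SD at τ = 1.0 and 0.154 SD at τ = 0.6. In SDs of the raw outcome, the first becomes 0.196√(2(1 − ρ)): 0.23, 0.20, 0.15 or 0.12 for an assumed within-person correlation ρ of 0.3, 0.5, 0.7 or 0.8.

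Mean 95% CI half-width: 0.70 SD paired and 0.71 SD adjusted with no shift; 0.79 SD paired and 0.71 SD adjusted at a shift of 0.5.

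**One dropout (5/4), τ = 1.0.** Adjusted power is 72.5% at any shift. Paired power depends on which order loses the participant:

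| Shift (SD) | Paired, favourable loss | Paired, unfavourable loss |
|---|---|---|
| 0 | 74.8% | 74.8% |
| 0.25 | 74.8% | 70.1% |
| 0.5 | 70.7% | 60.4% |

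The average of the two at 0.5 SD is 65.5%. Break-even is 0.41 or 0.15 SD, and 0.24 on average. The paired estimate is now biased by π(5 − 4)/9, one ninth of the shift with either sign: 0.056 SD at π = 0.5, against a standard error of at least 1/√9 = 0.33 SD. The adjusted estimate is unbiased.

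**The case against.** The strongest reply is that the loss depends on a quantity the documents never give. No section reports or implies a session effect. Practice on the incentive task need not matter, because the outcome is the signal to the $5 cue, not task performance. Below the break-even the proposed analysis has less power than the planned one, and just above it the gain is slight: 0.8 points at 0.25 SD. Shifts of 0.75 to 1.0 SD would be nearly as large as the assumed drug effect. A paired t-test on a counterbalanced crossover is a legitimate, conservative choice for a pilot.

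All of that stands, and it limits the point to efficiency. It does not reverse the balance: the most the period term can cost at 5/5 and effect 1.0 is 1.3 points, while at a 0.5 SD shift it saves 7.0.

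Three narrower objections are also fair:

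- A period term does nothing about carryover; the constant 79.1% assumes there is none.
- Normality has not been examined for greatest expenditure on the purchase task, which is drinks multiplied by one of 14 listed prices. The planned t-test makes the same assumption.
- Picture set also differs between scans in the Emotion Regulation task, and a period term does not remove a difference between sets.

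None of these undoes the gain from removing a period shift.

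**Conclusion.** The concern holds as an inexpensive improvement. The plan counterbalances order and then leaves it out of the analysis, so any session shift becomes error. The planned test is not invalid: with balanced complete data its estimate is unbiased, and its type I error was at or below 5% in every case computed.

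At 5/5 and an effect of 1.0 SD, the period-adjusted analysis is better once the shift exceeds about 0.20 SD of the paired difference. That threshold is specific to those conditions: it is 0.15 SD at effect 0.6, and 0.15 or 0.41 SD after one dropout. The bias after one dropout is small. The calculations rest on normal differences, no carryover and an assumed range of shifts. The arithmetic is firm; whether a shift of that size will occur is unknown.

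**What to change.** In Section IV.F, replace the paired t-test for all three outcomes with the standard two-period, two-sequence crossover analysis: treatment and period as fixed effects, participant as a random effect. For participants with both scans this is the two-sample t-test comparing the two orders on half the period differences, with n − 2 degrees of freedom. Name that as the primary analysis and report the treatment estimate with its 95% CI. If a mixed model is also fitted to include anyone with only one scan, label it a sensitivity analysis and use Kenward-Roger degrees of freedom. Do not pre-test for carryover.

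Fix the wording before treatment order is revealed, so that the choice is not guided by the data. Nothing new has to be collected, since the Investigational Drug Service already holds each person's order.

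The cost is one error degree of freedom. With no shift and an effect of 1.0, power falls from 80.3% to 79.1% at 5/5 (1.3 points before rounding) and from 74.8% to 72.5% at 5/4 (2.3 points). At 5/4 with a shift of 0.25 SD, neither method is uniformly better.

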Our goal is to better understand the neurobiology of reward processing by probing other neurotransmitter systems that interact with dopamine to regulate reward. The objective of this application is to establish whether healthy adults show reduced reward-related activation in the nucleus accumbens when ramped up to steady state dosing with naltrexone. Naltrexone is a mu-opioid antagonist and one of three medications approved by the Food and Drug Administration for the treatment of alcohol use disorder. We will also examine threat processing as a control paradigm to establish that opioid modulation primarily affects reward processing. Since diminishing reward signaling may reduce incentive to seek alcohol, we will also examine a measure of subjective alcohol evaluation. We are prepared to conduct this study based on our expertise in psychopharmacology and functional MRI studies of reward and threat processing as well as psychiatric disorders. This qualified group of investigators will make certain that our research adheres to both neuroscientific theory of reward processing as well as clinical application.

III. Preliminary Studies/Progress Report:

In a currently ongoing study, we have recruited 45 adults to complete the monetary incentive delay task and we have shown a strong main effect of cue type in nucleus accumbens activation ($F_{2,210} = 58.8, p < 0.001$), where activation is greatest during cues to gain \$5 (Figure 1).

[figure not shown]
[figure not shown]

Figure 1. Using the monetary incentive delay task, we found a main effect of cue on nucleus accumbens activation ($F_{2,210} = 58.8$, $p < 0.001$).

IV. Research Methods

A. Outcome Measure(s): There are three outcomes for this study: nucleus accumbens activation to monetary reward, amygdala activation to threat, and subjective alcohol evaluation. For nucleus accumbens activation, we will use percent signal change in response to the cue to earn \$5 during the Monetary Incentive Delay task. For the amygdala response to threat, we will use the percent signal change in response to negative images in the Emotion Regulation task. For the valuation of alcohol, we will use the Alcohol Purchase Task to assess the greatest expenditure on drinks (price paid multiplied by number of drinks).

B. Description of Population to be Enrolled:

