- a. **Recruitment, sample description and inclusion/exclusion criteria.** Participants will be recruited through advertisements on social media, paper flyering, advertising on local list-servs, and by peer recruitment. Our lab has successfully attracted over 340 participants to complete our screening measures using these methods in the past year. Interested individuals can contact the laboratory via email or phone call to arrange a phone screen, where we will assess likely eligibility for the study.
 - i. **Inclusion criteria:** A) Between 18 and 35 years of age,
 - ii. **Exclusion criteria:** A) AUDIT Score less than or equal to 14, B) Non-drinker C) positive result on urine drug screen or breathalyzer at the start of any study visit, D) inability to complete MRI (e.g. presence of ferromagnetic objects in body), E) current use of medications that alter the hemodynamic response, such as insulin, F) history of trauma resulting in loss of consciousness longer than 15 minutes, G) for females, pregnancy, H) current (within the last 3 months) use of opioids to avoid acute precipitated withdrawal due to opioid receptor antagonism I) treatment for a DSM5 disorder other than anxiety or depression through therapy J) treatment for a DSM5 disorder through medications, K) greater than 10 uses of illicit substances in the last year.
- b. **Feasibility:** We have recruited 45 participants to our laboratory's studies in the past year and conducted 45 MRI scans. To recruit ~10 participants in one year, we need to recruit 1 participant per month and conduct 2 scans per month. This is well within the capacity of our laboratory operations.

C. Study Design and Research Methods. After completing an informed consent procedure, participants will sign a consent form. They will then complete a psychiatric interview and receive 5 capsules. Participants will return five days later for visit 2. On visit 2, they will complete a medication side-effect questionnaire. If they report side effects that are more

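### The only prespecified check that a fall in accumbens signal is reward-specific is a null-predicted amygdala test in another task at n = 10; no reference region within the reward task is named

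*Combined protocol and SAP*

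**What the plan says.** Section IV.A defines the reward outcome: "we will use percent signal change in response to the cue to earn" $5 in the Monetary Incentive Delay task. Section IV.F compares each outcome between active medication and placebo by paired t-test. In preprocessing, "values will be scaled to have a mean intensity of 100". For the reward task, "activation will be extracted from the nucleus accumbens for each of the three cues". For the emotion task, "activation will be extracted from the amygdala for each of the three conditions".

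The plan does include a control. Section II says: "We will also examine threat processing as a control paradigm to establish that opioid modulation primarily affects reward processing". Section I gives this its own aim, and Hypothesis 2 predicts no drug effect on threat activation. Section IV.F adds a whole-brain voxel-wise analysis, labelled exploratory.

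Exclusion criterion E in section IV.B bars "current use of medications that alter the hemodynamic response, such as insulin". Section IV.E (potential scientific problems) discusses only that receptor binding is not observed, and argues that randomisation still supports attributing changes to naltrexone. Section IV.G hopes to show both that reward response is diminished and that the effect is specific to ventral striatal reward activation.

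The documents contain no drug-by-region or drug-by-cue test, no interval or equivalence margin for the amygdala result, no sensory or motor reference region, and no calibration of the BOLD response.

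**The concern.** Percent signal change reflects neural activity multiplied by the size of the BOLD response per unit of activity. Each participant has one scan on naltrexone and one on placebo. If the drug lowered BOLD responses everywhere by a common factor, the accumbens response would fall with no change in reward processing. Criterion E shows that the protocol regards drug effects on the hemodynamic response as a threat to its imaging outcomes, but the documents do not discuss the question for the study drug.

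Randomisation supports the statement that naltrexone lowered the accumbens signal. It does not show that the fall is particular to reward, which is the second conclusion section IV.G seeks. That conclusion rests on a significant accumbens result beside a non-significant amygdala result. With 10 pairs, that combination can easily arise when both regions have changed.

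**Working it through.** **1. The plan's own power figure.** Section IV.F states 80% power with 9 adults for an effect size of 1.0 at two-sided alpha 0.05. By the exact paired t-test (noncentral t, n - 1 df), power is 0.748 at n = 9 and 0.803 at n = 10. The planned 10 participants do give 80% power. The same calculation is used below.

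**2. What scaling and subtraction remove.** Multiply all responses by k. The $5-cue response changes by (k - 1) × gain, and the gain-minus-neutral contrast by (k - 1) × (gain - neutral). With assumed responses of 0.30 and 0.10 and k = 0.8:
- gain: -0.2 × 0.30 = -0.06
- gain minus neutral: -0.2 × 0.20 = -0.04

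Both fall by 20%. Scaling each series to a mean of 100 sets the baseline unit and leaves k untouched.

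**3. Effect on Hypothesis 1 (illustration).** Assumptions: no change in reward processing; mean $5-cue response of 2.0 between-person SD; between-session correlation r of 0.3-0.7; n = 10. The value 2.0 is prompted by the Cohen's d above 2.0 in section IV.C.b.i, but that section gives neither the contrast nor the SD behind it, so treating it as mean over between-person SD is an assumption.

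Paired effect = (fall × 2.0) / √(2(1 - r)).

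| General fall | r = 0.3 | r = 0.5 | r = 0.7 |
|---|---|---|---|
| 20%: effect | 0.34 | 0.40 | 0.52 |
| 20%: H1 significant | 16% | 21% | 31% |
| 30%: effect | 0.51 | 0.60 | 0.77 |
| 30%: H1 significant | 30% | 40% | 59% |

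The formula keeps the active-session SD at its placebo value. If the SD shrinks with the mean, the SD of the difference is √(1 + k² - 2kr). For k = 0.8 and r = 0.3 this is √1.16 = 1.08, and the effect is 0.40/1.08 = 0.37 instead of 0.34, so the table is slightly low.

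**4. How well the amygdala test would reveal a general fall.** The 95% half-width at n = 10 is t(0.975, 9)/√10 = 2.262/3.162 = 0.72 SD of the paired differences. Now suppose a general fall produces an effect of 1.0 in the accumbens and a smaller or equal one in the amygdala (assumed; the documents give no SDs). The simulation used 200,000 runs, with the correlation between the regional differences at 0.5 or 0.

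| Amygdala effect | Power of amygdala test | Amygdala non-significant, given a significant accumbens fall |
|---|---|---|
| 0.3 | 0.14 | 84-86% |
| 0.5 | 0.29 | 66-71% |
| 0.8 | 0.62 | 32-38% |
| 1.0 | 0.80 | 15-20% |

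The planned control can expose a general fall, but not reliably unless the amygdala effect is large.

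**5. What a within-task reference would need.** A rule that only asks whether the accumbens fell by a larger percentage than visual cortex does not work. In simulation of the step 3 model (visual response 2-3 SD, between-region correlation 0-0.5), with a purely general 20-30% fall, 61-93% of significant H1 results would still be labelled reward-specific, because significant results are selected for large accumbens falls. Requiring the 95% interval for the between-region difference to exclude zero holds the error in that direction near 0.05/2 = 2.5%.

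The price is power. Take a true accumbens effect of 1.0, no visual change, uncorrelated regional differences and a visual response of 2-3 SD. In percentage units the visual difference has q = 2/2 = 1 to 2/3 of the accumbens SD. The effect for the between-region difference is 1/√(1 + q²) = 0.71 to 0.83, with power 0.51 to 0.65. Requiring H1 to be significant as well gives about 48-63%, against 80% for H1 alone. Positive correlation between regions would raise this: at correlation 0.5 and q = 1 the SD is √(1 + 1 - 1) = 1 and the effect returns to 1.0.

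**The case against.** The strongest reply is that the plan already has a control. Threat processing is declared as one, with its own aim and hypothesis, and a fall in all BOLD responses should also lower the amygdala response and contradict Hypothesis 2. The whole-brain analysis also covers visual and motor cortex. A reader might therefore infer from this point that the plan has no control region, or that a general fall would pass without any check. The documents do not support either reading. What remains is that the control is a different task, is predicted null, has 10 pairs and no margin or interval, and that the whole-brain analysis names no region in advance.

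A second reply is that nothing in the documents says naltrexone alters BOLD responsiveness. That is correct. Criterion E concerns other medications and does not imply that naltrexone is one of them. Section IV.D.d lists sleepiness and dizziness as side effects, which makes an arousal route conceivable, but an arousal effect is neural and need not scale all regions equally.

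Third, the 16-59% counts Hypothesis 1 alone. If the control region had the same standardised response as the accumbens, a significant H1 with a non-significant control would occur in about 10-24% of trials. That is a fair qualification. The amygdala's actual response size is unknown, and step 4 shows that a weaker response makes the control less informative.

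Finally, this is a 10-person pilot that speaks of what it hopes to show. That limits the weight of the point, but the pilot data are meant to support a grant application, and specificity is one of the stated aims.

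**Conclusion.** The point holds in a limited form. The accumbens test cannot by itself separate a reward-specific fall from a general proportional fall in BOLD responses. Neither scaling nor cue subtraction helps, and the one prespecified check is too imprecise for its non-significance to establish specificity (half-width about 0.72 SD of the paired differences).

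The size of the threat is hypothetical. The 16-59% rests on an assumed general fall of 20-30%, a mean response of 2 between-person SD and r of 0.3-0.7, none of which the documents establish for this comparison. Nor should these rates be read as an inflated type I error: if naltrexone lowers the measured response, the paired null is false and attribution to the drug stands, as section IV.E argues. What is at issue is the word specific. This is an inexpensive improvement to what the trial can conclude, not a flaw that invalidates Hypothesis 1.

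**What to change.** In section IV.F:

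1. Prespecify extraction of the primary visual cortex response to the neutral cue from the same reward-task regression. The cue is visual and carries no money.
2. Report the active-minus-placebo differences for accumbens, visual cortex and amygdala, each with a 95% confidence interval and as a percentage of that region's mean placebo response.
3. Report the accumbens-minus-visual difference in percentage change with its 95% interval. One way is to divide each participant's differences by the region's mean placebo response, subtract within participant, and form the paired t interval.
4. Describe an accumbens fall as reward-specific only if that interval excludes zero in the direction of a larger accumbens fall. Otherwise report a reduced accumbens signal under naltrexone, with specificity not established. A comparison of point estimates is not enough.
5. State that a non-significant amygdala result will not be read as proof of specificity.
6. State the assumption that accumbens and visual cortex share a common proportional BOLD factor and that naltrexone has no separate neural effect on visual cortex.

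The cost is one more region from scans already planned and a few lines of text, with no added scan time or participants. The downsides are one more reported comparison, a specificity claim that is harder to reach at n = 10 (about 48-63% power in the illustrative case where H1 has 80%), and reliance on the assumption in item 6.

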COMIRB Protocol

COLORADO MULTIPLE INSTITUTIONAL REVIEW BOARD
[name] [contact] [contact]

Protocol #: 21-2886

Project Title: Opioid Modulation and Neural Reward Activation in Healthy Adults

Principal Investigator: [name]

Version Date: 10/28/21

I. Hypotheses and Specific Aims:

1. Evaluate whether mu-opioid receptor blockade via naltrexone alters reward activation in the ventral striatum. In a study of 10 healthy, moderate drinking adults, we will use a crossover design to examine brain activation during a functional MRI scan during placebo and mu-opioid blockade.

Hypothesis 1. Relative to the placebo scan, participants will show reduced reward-related activation in the ventral striatum during the active medication scan.

2. Evaluate whether mu-opioid receptor blockade alters threat activation in the amygdala. In the same sample and design from Aim 1, we will use the Emotion Regulation Task to assess threat related activation in the amygdala during a functional MRI scan.

Hypothesis 2. Opioid receptor modulation will not affect threat related activation, consistent with naltrexone primarily targeting reward motivation.

3. Examine whether mu-opioid receptor blockade via naltrexone alters valuation of alcohol. In the same sample and study design from Aim 1, we will use the Alcohol Purchase Task to assess subjective value of an alcoholic beverage in order to link opioid-modulation directly to alcohol motivation.

Hypothesis 3. Relative to the placebo session, participants will be willing to pay less money for an alcoholic beverage during the active medication session.

This proposal aims to fill a gap in understanding how endogenous opioid function affects reward response in the brain. One of the leading hypotheses is that individuals who drink to maximize reward are more likely to benefit from naltrexone treatment, and the current proposal would provide evidence for this in a healthy sample. Further, this work could lead to a clinical study of reward-related brain activation and response to naltrexone treatment in adults with an Alcohol Use Disorder. This stands to improve precision medicine approaches to tailor treatments for alcohol use disorder.

II. Background and Significance:

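### The stated 80% power with 9 adults is not reproduced: on the usual paired scale, 9 adults give 74.8% for an effect size of 1.0 and 10 are needed (minor correction)

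*Combined protocol and SAP*

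**What the plan says.** Section IV.F (Data Analysis Plan) compares active medication with placebo by paired t-test. The sample-size paragraph in the same section gives the error rates: "We specified significance level alpha=.05, two-tailed, and power of 0.8". It ends: "A sample of 9 adults would provide 80% power to detect an effect size of 1.0 or greater as significant".

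Two effect sizes come before that sentence, both given only as Cohen's d:

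- Above 1.0, where "a study of mice estimated a large effect size of mu-opioid antagonism on reward response in the nucleus accumbens".
- 0.6, where "A study of kappa-opioid receptor modulation in human reward response measured with functional MRI found a medium to large effect size".

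The paragraph does not say how d is standardised. It gives no standard deviation, within-person correlation, formula or software.

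Planned enrolment is 10. Section I, Aim 1 reads "In a study of 10 healthy, moderate drinking adults, we will use a crossover design", and Section IV.B.b (Feasibility) reads "To recruit ~10 participants in one year". No allowance for dropout is stated.

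**The concern.** The paragraph and the analysis plan together supply everything a paired power calculation needs: test, alpha, sidedness, sample size, effect size and target power. A reader should be able to reproduce 80% from them. With the usual meaning of effect size for a paired t-test, the result is below 80%.

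With 10 planned and 9 said to be enough, the text implies that one participant can be lost without falling under the target. Each participant must complete two scans, and Section IV.B.a excludes for a positive drug screen or breathalyzer at the start of any visit, so a loss is plausible. Section IV.G also says the pilot data will support a later grant application, where the same power statement could be carried forward.

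**Working it through.** **Inputs.** All are from Section IV.F except the planned enrolment of 10 (Sections I and IV.B.b):

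- paired t-test, df = n − 1
- alpha 0.05, two-sided
- n = 9
- effect size 1.0
- target power 0.80

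**Formula.** Let dz be the mean difference divided by the SD of the differences. The test statistic then follows a noncentral t distribution with df = n − 1 and noncentrality dz × √n. Power is the probability that its absolute value exceeds the 0.975 quantile of central t on n − 1 df.

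**Attempt to reproduce the plan's figure.** With n = 9 and dz = 1.0, the noncentrality is 1.0 × √9 = 3.0 on 8 df. Power is 0.748, not 0.80. Simulation of 400,000 paired t-tests gave 0.749.

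| n | Power at dz = 1.0 |
|---|---|
| 8 | 68.1% |
| 9 | 74.8% |
| 10 | 80.3% |
| 11 | 84.8% |

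Solving for 80% power gives n = 9.94, so 10. Turned round, the effect detectable with 80% power is dz = 1.07 at n = 9 and 0.996 at n = 10.

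**Other conventions at n = 9, effect 1.0.** None gives 80%:

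| Method | Power |
|---|---|
| One-sided paired t | 86.2% |
| Two-sided normal approximation | 85.1% |
| One-sided normal approximation | 91.2% |
| Crossover t with a period term (df = n − 2) | 73.1% |
| Two-sample t, 9 per arm | 51.3% |

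Solved for n, the simple normal approximation gives 7.85, so 8. With the usual small-sample correction it gives 9.77, so 10. Neither gives 9.

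**If 1.0 is on the within-condition SD scale.** With equal SDs in the two conditions and within-person correlation r, dz = d / √(2(1 − r)). Setting d = 1.0 and solving for the dz that gives 80% power yields r = 1 − 1/(2 dz²):

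- n = 9: 1 − 1/(2 × 1.067²) = 0.561
- n = 10: 1 − 1/(2 × 0.996²) = 0.496

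The plan states no correlation. Over an assumed range of 0.3 to 0.7:

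| r (assumed) | dz | Power, n = 9 | Power, n = 10 |
|---|---|---|---|
| 0.3 | 0.845 | 60.5% | 66.3% |
| 0.5 | 1.000 | 74.8% | 80.3% |
| 0.7 | 1.291 | 92.2% | 95.1% |

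At r = 0.5 the two scales coincide, because 2(1 − 0.5) = 1.

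**The case against.** The strongest reply is that the sentence is unverified rather than false. The only effect-size measure the plan names is Cohen's d, the 1.0 plainly echoes the mouse figure in the same paragraph, and Cohen's d is often standardised by the within-condition SD. On that reading 9 adults do reach 80% once the within-person correlation is about 0.56, and they reach 83.5% at 0.60. How the cited studies standardised d cannot be seen from the documents. This stands as far as it goes, and it is why the conclusion is conditional on the scale. It does not rescue the sentence, because the plan states neither that scale nor a correlation. Both readings lead to the same repair.

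A second reply is that the consequence is close to nil: enrolment is 10, the error is one participant, and this is a pilot. That stands, and it sets the weight at minor.

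A third is that saying enrolment need not change goes too far. This stands in part. Ten is enough on the SD-of-differences scale only if all 10 are evaluable, and on the within-condition scale 10 falls below 80% for any correlation under 0.496.

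The words allowing for an effect larger than 1.0 do not help either. The value 1.0 is the lower boundary of the claim, and on the usual scale power is below 80% for effects from 1.0 up to 1.07.

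**Conclusion.** The concern holds, as a minor correction. For the planned two-sided paired t-test at alpha 0.05, with 1.0 taken as mean difference over SD of differences, power at 9 is 74.8%, or 5.2 points below the stated 80%. Ten participants are needed, and they give 80.3%. Losing one of the 10 returns power to 74.8%. On the within-condition scale the stated 80% would need a correlation of about 0.56, which the plan does not give. These figures rest on normally distributed differences and, for the second scale, on equal SDs in the two conditions. The planned analysis is not affected.

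**What to change.** Replace the sentence with one to this effect: *10 evaluable participants give 80% power for a paired effect size (mean difference divided by SD of differences) of 1.0; 9 give 75%.*

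If another scale was meant, state that scale and the within-person correlation assumed, and recompute.

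The correction alone needs no change in enrolment, provided the SD-of-differences scale applies and all 10 complete both scans. The cost is rewording one sentence, with a slightly less favourable figure for 9.

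Optionally, report power for the 0.6 from the cited human study, noting that it concerns kappa-opioid modulation and not mu-opioid blockade. With 10 participants this is about 40% on the SD-of-differences scale, or 30% to 59% on the within-condition scale for assumed correlations of 0.3 to 0.7. This concerns the choice of planning effect, a separate matter from the arithmetic.
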